**5 a) Describe how and where informed consent will be obtained?**

Singed informed consent will be obtained from the parents or legal guardian of the subjects at household. Contents of the consent form will be read in *Bangla*.

**5 b) If information is to be withheld from a subject, justify this course of action?**

There is hardly any information to be withheld. However, the subjects will be explained that they are randomized to receive one of the three types of blended fish, *mola*, *ru* and *ru with added vitamin A* dishes.

They will be informed that two of the fish dishes will contain vitamin A and one fish dish will contain Low/ no vitamin A. However neither the subjects/ mothers nor the study staff will know which type of fish dish they are going to receive during the feeding trial. This is done in order to eliminate bias.

**5 c) Stating whether or not a compensation and / or treatment will be available?**

There is no potential risk to the subject or privacy of the individual is involved.

Children who do not fulfill the health examination, show clinical sign of vitamin A deficiency, have serum retinol concentrations  $< 0.35 \mu\text{mol- L}$  or show any clinical sign of sickness (high fever, ARI, measles, dysentery etc) during the feeding trial will be not be included in the study and referred to the medical doctor for treatment. All children will be given anti-helminthes treatment before the study. The families of the children will have access to the available services of the medical doctor at the ICDDR, B local Mirpur office. At completion of the feeding trial, the children will be given a recommended oral vitamin A dose and other supplementation and anti-helminthes agents as medically advisable.

**6. Interviews: Describe where and in what context the interview will take place. State approximate length of time required for the interview.**

- a) Identification of household and 3-7 yrs. Children to be included in the study – at household levels: once (5 min.)
- b) SES information at the household level – once (30 min.)
- c) Semi quantitative Dietary assessment of vitamin A rich food at household – once (20 min.)
- d) Dietary intake assessment by 24 h. recall fortnightly – 6 times at household (15 min.)
- e) Morbidity – baseline at the household and then 5 times more during 9 weeks (10 min.)
- f) Child clinical health examination 5 times at the sub- centre (20 min.). Based on needs, children may be examined by the study physicians.

Mothers perception about *mola* fish will be assessed using both structured and open-ended questionnaire. This may take 10 mints. In addition, focus group discussion with 10-15 mothers at 3-4 sessions at the subcentre can be organized.

Physicians, nurses and RESEARCH/HEALTH assistants at the local centre will perform clinical health examination, anthropometry measurement and blood collection at screening, baseline and endpoint (lasting about  $\frac{1}{2}$  h each time).

**7. Assess benefits to be gained by the individual subject, the society in general, and how the benefits outweigh the risks**

All potential children will get a free health examination by physician and diagnostic if necessary as well as free deworming medication and vitamin A supplementation. Children will also be identified if they have severe or marginal deficiency based on serum retinol.

All children enrolled in the feeding trail will be served by lunch containing rice, fish curry and vegetable curry each day 6 days a week for 9 weeks. At the completion of the trial, children will be given vitamin A supplementation as medically advised.

The families of the subjects will have access to the available services of the medical doctor at the ICDDR,B local Mirpur office.

If the study is a success, it is valuable as a first step towards improving the production, availability, accessibility and intake of vitamin A rich small fish in the community. Hence, the study may help to improve vitamin A deficiency in people in the community as well as millions of other people who suffer from vitamin A deficiency.

**8.State if the activity requires the use of records (hospital, medical birth, death or other), organs, tissues, body fluids, the fetus or the arbortus?**

The activity does not require use of records. However, blood for measurement of vitamin A, iron status, protein and acute phase protein levels; and stool for presence and load of worms will be collected.

CENTRE FOR HEALTH AND POPULATION RESEARCH

Mail : ICDDR,B, [name]

[contact], Telex : [name] ICDD BJ

[contact], [name], [name], [name], Cable : Cholera Dhaka

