5. Yes, you are right. Our primary aim is the improvement in retinol status and accordingly sample size was calculated. For the other variables, data analysis plan has been described in page 21 of the protocol. Also handling of confounding factors are discussed in page 16.
6. We made it descriptive so that most questions are clear to the consent giver.
7. Please find now the Bangla version of the consent form.
8. It was an inadvertent mistakes. The serial number 10 and 11 would be 8 and 9. A corrected version is enclosed.
9. Thank you very much for pointing out the typo-error and few mistakes. The spelling errors are now corrected. Fresh abstract summary and consent form are also enclosed.

We hope, the protocol may please be approved now.

*I have gone through the responses by the investigators. The issues have been addressed and the protocol may be approved.*

*[name]*  
*03/12/2001*

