**5c) Stating whether or not a compensation and/or treatment will be available?**

There is no potential risk to the subjects or privacy of the individual is involved.

Children who do not fulfil the health examination, show clinical sign of vitamin A deficiency, have serum retinol concentrations < 0.35mmol/L or show any clinical sign of sickness (high fever, ARI, measles, dysentery etc) during the feeding trial will not be included in the study and referred to the medical doctor for treatment. All children will be given anti-helminthic treatment before the study.

The families of the children will have access to the available services of the medical doctor at the ICDDR, B local Mirpur office. At completion of the feeding trial, the children will be given a recommended oral vitamin A dose and other supplementation and anti-helminthic agents as medically advisable.

**6. Interviews: Describe where and in what context the interview will take place. State approximate length of time required for the interview.**

- a) Identification of household and 3-7 yrs. children to be included in the study – at household levels: once (5 min.)
- b) SES information at the household level – once (30 min.)
- c) Semi quantitative Dietary assessment of vitamin A rich food at household – once (20 min.)
- d) Dietary intake assessment by 24 h. recall fortnightly – 6 times at households (15 min.)
- e) Morbidity – baseline at the household and then 5 times more during 9 weeks (10 min.)
- f) Child clinical health examination 5 times at the sub-centre (20 min). Based on needs, children may be examined by the study physicians

Mothers perception about mola fish will be assessed using both structured and open-ended questionnaire. This may take 10 mins. In addition, focus group discussion with 10-15 mothers at 3-4 sessions at the subcentre can be organised.

Physicians, nurses and local assistants at the local centre will perform clinical health examination, anthropometry and blood collection at screening, baseline and endpoint (lasting about ½ h each time).

**7. Assess benefits to be gained by the individual subject, the society in general, and how the benefits outweigh the risks**

All potential children will get a free health examination by physician and diagnostic if necessary as well as free deworming medication and vitamin A supplementation. Children will also be identified if they have severe or marginal deficiency based on serum retinol.

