### Design and intervention groups

A house to house survey will be conducted in about 4 camps purposely selected in order to achieve proposed target children (inclusions criteria in points 1-4 on the next page and **Appendix 1: Household mapping form**).

For the intervention study only marginal vitamin A deficient children (based on serum retinol concentrations 0.35-0.70  $\mu\text{mol/L}$ ) will be selected, since only in these children is the intervention expected to have an increase in serum retinol concentration. Expecting that one out of three children (33%) has marginal vitamin A deficiency, approximately 550 children who meet the inclusion criteria listed in points 1-7 below, will be *screened* to determine their serum retinol concentration.

Children who meet all of the following inclusion criteria will be selected for *screening*:

1. Preschool children of both sexes between 3 and 7 years of age from families of lower socio-economic status
2. Children who eat fish
3. Taking no vitamin A supplementation and multivitamin in the preceding 6 months
4. Not suffering from serious illness like: persistent or chronic diarrhoea, tuberculosis, chronic pneumonia disease, asthma, diabetes type 1, hepatitis B, cardiac malformation, measles, respiratory tract infections, acute diarrhoea and skin infections
5. Parents and children who give their consent to participate in the study
6. Children who pass the clinical health examination (Appendix 2: Child clinical health examination form): For example having no clinical signs of vitamin A deficiency, chronic diseases, measles, respiratory tract infections, acute diarrhoea, skin infections and severe malnutrition
7. On the time of blood drawing, have no fever and show no clinical sign of acute infections, including diarrhoea

Children (n=180) identified as marginal vitamin A deficient (based on serum retinol concentrations 0.35-0.70  $\mu\text{mol/L}$ ), will be randomly allocated to either of the following three intervention groups and enrolled in the feeding trial at *baseline*. In each intervention group, there will be 60 children, receiving the same basic meal and either:

- 1) small fish, mola (vitamin A rich group) or
- 2) big fish, rui (negative control group, no/low vitamin A) or
- 3) rui and purified vitamin A, retinyl palmitate (positive control group)

All children will receive one meal per day, replacing one of the meals at home for 6 days a week for 9 weeks.

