#### ***Endpoint***

At *endpoint*, children will be clinically health examined and anthropometry will be recorded (Appendix 2: Child clinical health examination form). One blood sample will be collected from all children. An additional blood sample will be collected for the RDR test. This will be done on a subsample of children (15) in each of the 3 intervention groups.

At the completion of the feeding trial, all children will be supplemented with vitamin A.

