### **Morbidity**

The incidence of infection: diarrhoea, dysentery, upper acute respiratory infection, pneumonia, fever, measles, night blindness, vomiting, ear and eye infections, within the last 30 days will be recorded once per screened child, in connection with the collection of *baseline* information (550 children) (Appendix 6). The data will be used for the assessment and relationships between outcome parameters.

For the children (n=180) enrolled in the feeding trial, morbidity (incidence within the last 2 weeks) will be registered biweekly between *baseline* and *endpoint*. The results will be used to calculate mean morbidity (based on 4-5 registrations) in each intervention group during the feeding trial.

Below are description of common morbidity:

URI	Presence of cough and or nasal discharge
ALRI (Pneumonia)	Presence of cough and tachypnoea (>40 resp/min) with or without chest indrawing
Diarrhoea	3 or more loose stools in 24 hours
Dysentery	Loose stools with blood or blood with mucus
Fever	>38 0c body temp.

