## Ethical Assurance for Protection of Human Rights

Describe in the space provided the justifications for conducting this research in human subjects. If the study needs observations on sick individuals, provide sufficient reasons for using them. Indicate how subject's rights are protected and if there is any benefit or risk to each subject of the study.

Vitamin A deficiency is still a major public health problem in the developing countries. Previous studies in the proposed site indicated that > 50 % preschool children have subclinical deficiency based on serum retinol. The children and their parents will be informed and explained orally and in writing about the purpose and procedures of the study. Parents of children participating will give their written consent. Children who do not fulfil the health examination, show clinical sign of vitamin A deficiency, have serum retinol concentrations < 0.35mmol/L or show any clinical sign of sickness during the feeding trial will be referred to the medical doctor for treatment.

The following ethical considerations have been taken into account with respect to enrolling children in a negative control group (receiving big fish). The children will replace only one habitual meal per day by a no/low vitamin A rich meal, while all other meals will be consumed at home, as usual. The study will be conducted for a relatively short period, 9 weeks, 6 days per week. No severely vitamin A deficient children (serum retinol concentration <0.35mmol/L) will be recruited.

At completion of the feeding trial, the children will be given a recommended oral vitamin A dose and other supplementation and anti-helminthic agents as medically advisable.

The families of the children will have access to the available services of the medical doctor and treatment at the ICDDR, B local Mirpur office.

All children will be given anti-helminthic treatment before the study. In the study area, it has been found that >90% children are infected.

For conducting the RDR method extra effort and motivation will be done to keep the mother along with the child for extra 5 h during. During this time the child and the mother will be served beverage.

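### Read literally, the ethics summary excludes randomised children who fall ill during feeding, which conflicts with the operative plan to sample all children at endpoint and adjust for morbidity

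*Protocol*

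**What the plan says.** The Protocol contains two copies of the Abstract Summary for the ERC. Item 5 c) of one lists, among children to be left out and referred to a doctor, those who "show any clinical sign of sickness (high fever, ARI, measles, dysentery etc) during the feeding trial will be not be included in the study". Item 5c) of the other carries the same rule: "show any clinical sign of sickness (high fever, ARI, measles, dysentery etc) during the feeding trial will not be included in the study".

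This is current text. The investigators' reply to the ethics committee of 3 December 2001 (item 9) says "Fresh abstract summary and consent form are also enclosed", and approval followed on that reply.

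The sections that govern conduct and analysis read differently:

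- Design and intervention groups places illness criteria before entry. Criteria 4 and 6 cover serious illness and the clinical examination. Criterion 7 requires that children "On the time of blood drawing, have no fever and show no clinical sign of acute infections, including diarrhoea".
- Endpoint: "One blood sample will be collected from all children".
- Morbidity, for the 180 enrolled children: "morbidity (incidence within the last 2 weeks) will be registered biweekly" between baseline and endpoint.
- Confounding factors and Data Analysis adjust for morbidity during the study.
- Specific objectives, third objective, item e), asks whether diarrhoea, respiratory infection, fever and measles during the study affect the change in vitamin A status.
- Appendix 12, response 1.4.1, tells the funder's referee that children with clinical infection during the study will be kept.

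**The concern.** Removing children for illness that appears after allocation is not neutral. The section on biochemical indicators of vitamin A and iron status states that concurrent infection can lower serum retinol, the variable on which the trial is sized. The Background states that better vitamin A status reduces the severity of infectious illness. Illness could therefore relate both to the outcome and to the arm, and a comparison limited to children who stayed well would no longer be protected by randomisation.

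The trigger is also broad. Any sign of sickness counts, acute respiratory infection is named, and the Morbidity section counts cough or nasal discharge alone as upper respiratory infection. Field staff or a data manager working from the ethics summary could remove children whom the methods sections expect to be present at endpoint.

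**Working it through.** The question is whether the rule applies after randomisation and whether it can coexist with the rest of the plan.

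1. **Timing.** Allocation to the three groups takes place at baseline (Design and intervention groups; At baseline; Time schedule, end of February 2002). Feeding follows from mid March. A sign of illness that appears while feeding is under way therefore appears in a randomised child. Illness at entry is already covered by criteria 4, 6 and 7, so the clause is not needed as a screening rule.

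2. **Endpoint blood.** Endpoint plans a sample from every child, and the Time schedule expects about 180. If children were removed at the first sign of illness, this would not be so.

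3. **Morbidity covariate.** If every child with any sickness sign were removed, those left for analysis would have essentially no recorded morbidity. The covariate in Data Analysis would then have almost nothing to vary over, and item e) of the third objective could not be addressed.

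4. **Within the summary itself.** Item 6 e) schedules morbidity interviews "baseline at the household and then 5 times more during 9 weeks". That sits badly with removing children once they are ill, although well children could still be interviewed.

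5. **Earlier commitment.** Response 1.4.1 was written for an earlier draft with older children. The award letter (paragraph 2) nevertheless makes the changes listed in those responses a condition of the grant.

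6. **Can the effect be sized?** The plan's own figure reproduces: (1.96 + 1.28)² × (0.20² + 0.20²) / 0.15² = 37.3, stated as 37 per group. Allowing for 40% loss gives 37 / 0.60 = 61.7, stated as about 60. Going from 60 to 37 is a loss of 1 − 37/60 = 38%. The documents give no illness rate to set against this, so it shows no loss of power.

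7. **Can bias be shown?** Suppose the mean change in arm k is m_k for well children and m_k − g for ill children, with the same g in every arm. Comparing well children only gives m_1 − m_2. Comparing all children with an illness covariate also gives m_1 − m_2. A simulation used 60 per arm, a true difference of 0.15, SD 0.20, g = 0.10 and illness in 30% against 50% of children, with every illness input assumed. Over 4,000 runs it gave mean estimates of 0.149 (well children only) and 0.150 (all children, adjusted). The two rules can diverge if g differs between arms, and nothing in the documents says whether it does.

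**The case against.** The best defence is that the operative plan is already clear and the sentence is only badly drafted. It answers a form question about compensation and treatment, not about eligibility or analysis. The other conditions in the same sentence (failed health examination, clinical deficiency, retinol below 0.35 µmol/L) are entry failures, all governed by one verb about inclusion. The clause may be a garbled version of criterion 7. No section turns it into a withdrawal procedure.

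Most of this stands. The methods favour retention, and the documents do not support an inference that the trial chose to exclude children after randomisation. What does not fall away is the wording itself: it refers to the feeding period, appears in both copies and belongs to the approved ethics material.

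Two other inferences go too far:

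- A reader might take the Ethical Assurance section as proof that ill children stay, because there they "show any clinical sign of sickness during the feeding trial will be referred to the medical doctor for treatment" with no mention of removal. The same list includes children with retinol below the severe cut-off, who are certainly barred from enrolment. Silence there does not establish retention.
- A reader might take item 3 of the reply to the ethics committee, about taking children out and supplementing them, as confirming removal for illness. The conditions it refers to may be vitamin A supplementation in the previous six months, and the consent item it cites is not in the text at hand. It supports neither side.

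**Conclusion.** The conflict is real and should be corrected. A stated rule in the ethics summary, if followed, would exclude randomised children for a condition that affects serum retinol. The endpoint sampling, the morbidity recording, the adjustment and the third objective all presuppose that such children remain.

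The risk is conditional on someone acting on the ethics wording. Neither the direction nor the size of any bias can be stated, since the illness rate, its difference between arms and the retinol gap between ill and well children are all absent. A reader might infer a demonstrated bias or a loss of power; the documents show neither. The conclusion rests on the plain meaning of the clause about the feeding period and on the stated order of randomisation before feeding.

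**What to change.** Amend item 5 c) in both copies of the ethics summary so that acute illness bars entry only up to randomisation, in line with criteria 4, 6 and 7. Then state that a child who falls ill later:

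- is referred and treated, including vitamin A if medically needed, with the test meals stopped if necessary;
- stays in follow-up and has endpoint blood taken;
- is analysed in the randomised arm.

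This needs the ethics committee's approval of a wording change. It needs no extra visits, samples or data, because endpoint blood and two-weekly morbidity records are already planned for all 180 children. The one statistical cost is a slight dilution of the contrast between arms from children who receive vitamin A as treatment.

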## Memorandum

2 December 2001

To : Mr. [name]  
Laboratory Sciences Division

From: [name]  
Chairman, Ethical Review Committee (ERC)

Sub: **Protocol # 2001-025**

Thank you for your protocol # 2001-025 entitled "The efficacy of Vitamin A rich small fish in improving Vitamin A status in children in Bangladesh", which the ERC considered in its meeting held on 28th November 2001. After review and discussion in the meeting, the Committee made the following observations on the protocol:

- a) The study will not use many small fishes; rather a specific kind (Mola fish) will be used. Therefore, the title seems to be confusing. The appropriate title would have been "The efficacy of feeding a small fish ....."
- b) The basis of feeding for 9 weeks was not clear.
- c) It is assumed that Vitamin A is given normally by the Government VAC programme every six months to all children < six years, and also during the NID, ARI and diarrhoea episodes. Would the investigators deviate from the current Government policy?
- d) It was considered that the study should be done in a crossover design. That is those children with no/low Vitamin A diet should get Vitamin A capsules at the end of the study. This should also be clearly mentioned in the consent forms.
- e) The protocol has too many objectives and the sample size was calculated only on the basis of serum retinal. The Committee expressed concern that with this sample size, the effect of other variables such as iron status, morbidity, anthropometry, behavioural changes cannot be looked into.
- f) The consent form could be made more simple and understandable for the common people. Further, in the Bangla consent form protocol title and PI's name have been mentioned in English. In the consent form (point # 10), it has been mentioned that no penalty will be imposed for withdrawal of from the study, which was considered to be inappropriate. Indeed participation in the study is completely voluntary.

g) There are many spelling mistakes/typos. In the English consent form, (2nd part), points 8 and 9 were found to be missing.

You are, therefore, advised to address the above issues and to submit the modified version of the protocol incorporating the above observations for consideration of the Chair.

Thank you.

Copy: Acting Head  
Laboratory Sciences Division

To : Mr [name]

From : [name]

Subject: Bangla version of questionnaire

Enclosed pls find the Bangla version of questionnaire. These are awaiting pre-test and after that we shall get these finalized.

I am enclosing these, in case there are points raised by any ERC members.

Thanking you.

সংযোজন-২

শিশুর স্বাস্থ্য পরীক্ষা ফর্ম

শিশুর নাম:

প্রাথমিক ওষু

১। স্নানোত্তর আবিষ্কার

দিন	মাস	বর্ষ
-----	-----	------

২। শিশুর স্ট্যাডি নং

৩। শিশুর পরিচিতি নং

--	--	--	--

৪। স্নানোত্তর পরিচিতি নং

--	--	--	--

৫। ক্যান্সার নাম

--	--

৬। উত্তরদাতা/দায়ী

১। মা

২। বাবা

৩। অন্যান্য

৭। লিঙ্গ

১। পুরুষ ২। মহিলা

৮। জন্ম তারিখ (বাল্য/শৈশু/বয়স্ক)

দিন মাস বর্ষ

৯। জন্ম আবিষ্কার স্থান

--	--	--	--

১০। বয়স

১০ বছর

--	--	--	--

১১। উচ্চতা (সেমি)

--	--	--	--

১২। ওজন (কিগ্র)

--	--	--	--

১৩। স্বাস্থ্য বাধার ইতিহাস (হ্যাঁ/না)

--	--	--

টিকানাম

১৪। ডিপিপি১

১ = হ্যাঁ

২ = না

১৫। ডিপিপি২

১ = হ্যাঁ

২ = না

১৬। ডিপিপি৩

১ = হ্যাঁ

২ = না

১৭। ওপিডি১

১ = হ্যাঁ

২ = না

১৮। ওপিডি২

১ = হ্যাঁ

২ = না

১৯। ওপিডি৩

১ = হ্যাঁ

২ = না

২০। শাস

১ = হ্যাঁ

২ = না

২১। BCG

১ = হ্যাঁ

২ = না

শিশুর পরিচিতি নং

--	--	--	--

শিশুর স্ট্যাডি নং

--	--	--	--

অধিকার পরীক্ষা

২২। উদ্ভিতির স্বাস্থ্য

১ = স্বাস্থ্যবিক

২ = অস্বাস্থ্য

২৩। ফ্যাকাহু ডার

১ = নাই

২ = আছে

২৪। চাষভার অবস্থা

১ = সুস্বাস্থ্য

২ = অস্বাস্থ্য

৩ = অন্যান্য

২৫। বাসীর স্থিতি

--	--	--

বিনির্ধ

ଆଧ୍ୟାୟ- ୩

ଆକୃଷ୍ଟିକ- ଉଦାହରଣ ଡାଏଗ୍ରାମ ଡକ୍ଟ୍ରି, ସାମାଜିକ

ସାମାଜିକ ସାମାଜିକ ମିଶ୍ରଣର ଉଦାହରଣ ଓ ଏହାର ଉପକ୍ରମ ସମ୍ବନ୍ଧରେ ପ୍ରଶ୍ନମାନଙ୍କର ଉତ୍ତର

ଆମର ଆଧ୍ୟାୟିକା ଯତ୍ନ- ୧

୧. ସାମାଜିକ ଉଦାହରଣର ନାମ 

--	--	--
୨. ସାମାଜିକ ମିଶ୍ରଣର ନାମ 

--	--	--	--
୩. ସାମାଜିକ ମିଶ୍ରଣର ନାମ \_\_\_\_\_
୪. ସାମାଜିକ ମିଶ୍ରଣର ନାମ \_\_\_\_\_
୫. ସାମାଜିକ ମିଶ୍ରଣର ନାମ \_\_\_\_\_ କ୍ରମ ସଂଖ୍ୟା \_\_\_\_\_
୬. ସାମାଜିକ ମିଶ୍ରଣର ନାମ ଓ ସାମାଜିକ ମିଶ୍ରଣର ନାମ \_\_\_\_\_ / 

--	--	--	--
୭. ସାମାଜିକ ମିଶ୍ରଣର ନାମ ଓ ସାମାଜିକ ମିଶ୍ରଣର ନାମ \_\_\_\_\_ / 

--	--	--	--
୮. ସାମାଜିକ ମିଶ୍ରଣର ନାମ ଓ ସାମାଜିକ ମିଶ୍ରଣର ନାମ \_\_\_\_\_ / 

--	--	--	--
୯. ସାମାଜିକ ମିଶ୍ରଣର ନାମ ଓ ସାମାଜିକ ମିଶ୍ରଣର ନାମ \_\_\_\_\_ / 

--	--	--	--

ପାଠ୍ୟ ଆଖ୍ୟାୟିକା ଧ୍ୟୟନ-୪

ବାସ୍ତବ ପାରିଚିତ୍ତି ନୁ

କ୍ୟାନ୍ଧା ଟକାଠ

୧। ବ୍ୟବହୃତ ପାନିର ଉତ୍ସ

କ) ପାନୀୟ; ୧ = ଧାତୁକାଠା ଅବସ୍ଥା, ୨ = ବିଜ୍ଞ ସ୍ଥାୟିକ ଧାତୁ, ୩ = ଉତ୍ପତ୍ତି, ୪ = କୁମ୍ଭ, ୫ = ଅନ୍ୟ

- ଖ) ସ୍ନାତ୍ନା
- ଗ) ସାଧନପାତ୍ର
- ଘ) ଶୋଧନ
- ଙ) ଅନ୍ୟାନ୍ୟ

୨। ଆଧାନି ଯି ନିକ୍ଷକାଠର ଉତ୍ସ ପାନି ଅବସ୍ଥାନ କରନ ?

- କ) ପାନୀୟ    ୧ = ଧାତୁ    ୨ = ଧାତୁ
- ଖ) ସ୍ନାତ୍ନା    ୧ = ଧାତୁ    ୨ = ଧାତୁ
- ଗ) ସାଧନପାତ୍ର    ୧ = ଧାତୁ    ୨ = ଧାତୁ
- ଘ) ଶୋଧନ    ୧ = ଧାତୁ    ୨ = ଧାତୁ
- ଙ) ଅନ୍ୟାନ୍ୟ    ୧ = ଧାତୁ    ୨ = ଧାତୁ

୩. ପାନି ଅବସ୍ଥାନର ଉତ୍ସ ବ୍ୟବହୃତ ପାତ୍ରର ବିଧାନ

- ୧. ଧାତୁ ବାଳତି    ୧ = ଧାତୁ    ୨ = ଧାତୁ
- ୨. ସାଧନପାତ୍ର ବାଳତି    ୧ = ଧାତୁ    ୨ = ଧାତୁ
- ୩. ଧାତୁ ବାଳତି    ୧ = ଧାତୁ    ୨ = ଧାତୁ
- ୪. ଧାତୁ    ୧ = ଧାତୁ    ୨ = ଧାତୁ
- ୫. ଧାତୁ ପାତ୍ର    ୧ = ଧାତୁ    ୨ = ଧାତୁ
- ୬. ସାଧନପାତ୍ର ପାତ୍ର    ୧ = ଧାତୁ    ୨ = ଧାତୁ
- ୭. ଧାତୁ ପାତ୍ର    ୧ = ଧାତୁ    ୨ = ଧାତୁ
- ୮. ଅନ୍ୟାନ୍ୟ    ୧ = ଧାତୁ    ୨ = ଧାତୁ

ଆର୍ଥ-ସାମ୍ବାଦିକା କାହାଣୀ - ୫

ସାଜି-ପାଠିଚିତି-ନ;

ବ୍ୟାକ୍ଷା ଟିକା

୭) 28 ଶର୍ଯ୍ୟା ଆମାରି କହବା ପାରି ଅନ୍ୟ କହନ ? (ଅଧିକାର କାହାର ଜନ)

୮) ନିଜର ଶ୍ୟାସି-ପାରିର ନାରିନ ଟକାକାଠି ୧ = ପାଠ୍ୟାମା, 2 = ନକା, ୩ = ପାଠ୍ୟ  
୪ = ଅନ୍ୟ ନା

୯) ସାଧୁ ଆନୁଷ୍ଠାନ ନିଜର ଟକାକାଠିର ପାଠ୍ୟାମା ବ୍ୟବହାର କହନ ?

- |                                |                     |           |                 |          |
|--------------------------------|---------------------|-----------|-----------------|----------|
| କ) ପୁସ୍ତକ (୧ ବର୍ଷର ଡାକ)        | ନିର୍ଦ୍ଦିଷ୍ଟ ନା = ୧, | ଫାଳା = 2, | ଆକୃଷ୍ଟାକାର = ୩, | ଅର୍ଥ = 8 |
| ଖ) ଆଶିନା ( " " )               | "                   | "         | "               | "        |
| ଗ) ୧-୨ ବର୍ଷର ଟକାକାଠି           | "                   | "         | "               | "        |
| ଘ) ୩-୪ ବର୍ଷର ଟକାକାଠି           | "                   | "         | "               | "        |
| ଙ) ୫ ବର୍ଷର ନିର୍ଦ୍ଦିଷ୍ଟ ଟକାକାଠି | "                   | "         | "               | "        |

୧୦) ପାଠ୍ୟାମା ଅନ୍ୟାୟା କି ନିଜର ନା ଶ୍ୟାସି ପାଠ୍ୟାମା ବ୍ୟବହାର କହନ ?  
୧ = ନିଜର , 2 = ଶ୍ୟାସି

୧୧) ପାଠ୍ୟାମାୟ ଜୁଗା ବ୍ୟବହାର :

କ) ଜାଲିକାପୁସ୍ତକ ନିଜର କି ପାଠ୍ୟାମାୟ ଜୁଗା ବ୍ୟବହାର କହନ ?

- |                      |                          |        |
|----------------------|--------------------------|--------|
| ନିଜର ନିର୍ଦ୍ଦିଷ୍ଟ ନା; |  | ନା = 2 |
| ନିଜର ନିର୍ଦ୍ଦିଷ୍ଟ ନା; |  | ନା = 2 |
| ନିଜର ନିର୍ଦ୍ଦିଷ୍ଟ ନା; |  | ନା = 2 |

ଖ) ନିଜର ଟକାକାଠି ଅନ୍ୟାୟା :

ଗ) ନିଜର କହନ ଅନ୍ୟାୟା ପାଠ୍ୟାମାୟ ଜୁଗା ବ୍ୟବହାର କହନ

ଆର୍ଥ ଆନ୍ତର୍ଜାତିକ ସମ୍ବନ୍ଧ- ୧୬

କ୍ୟାମ୍ପ ଟ୍ରେକ

ସାମ୍ପ୍ରତିକ ପାରିଚ୍ଛିଦିତ୍ୟ

୧୩) ୨୦୦ ଟଙ୍କାର ଆର୍ଡରର ବିବରଣ:

ଉପଲବ୍ଧ	କିଲୋଗ୍ରାମ	କିଲୋଗ୍ରାମ	ପାଣିର ଓଡ଼ିଆ
କ) ଧାସ୍ୟର ଟିଆରୀର ପୂର୍ବ			
ଖ) ଧାସ୍ୟର ଅନ୍ତର ପୂର୍ବ			
ଗ) ପାସ୍ୟାନ୍ତର ପର			
ଘ) ଧାସ୍ୟର ଟିଆରୀର ପୂର୍ବ			
ଙ) ଅନ୍ୟାନ୍ୟ			

କିଲୋଗ୍ରାମ କାରା:  $ନା=0$       ପାଣି = ୦,      ଗ୍ରୀଷ୍ମ = ୨,      ଚାଉଁଶ = ୩,      ବାସନ୍ତ = ୫

କିଲୋଗ୍ରାମ :       $ନା=0$       ବାସନ୍ତ = ୦,      ଧାନ = ୨,      ଚାଉଁଶ = ୩,

ପାଣିର ଓଡ଼ିଆ: ୨ ପାଣିର ଓଡ଼ିଆ ଧାନର ପାଣି = ୦,      ଚାଉଁଶର ଓଡ଼ିଆ = ୩,      ଚାଉଁଶର ଓଡ଼ିଆର ପାଣିର ଓଡ଼ିଆ = ୨

କୂଳ = ୫,      ଅନ୍ୟାନ୍ୟ = ୫

କ) ଧାସ୍ୟର ପାଣିର ପାଣି କି ଧାନ- ଧାନ?       $ନା=0$        $ନା=2$

ଖ) ଅନ୍ୟାନ୍ୟ ଧାସ୍ୟର କି ଧାନ- ଧାନ?       $ନା=0$        $ନା=2$

ଗ) ବାସନ୍ତର ଧାସ୍ୟର କି ଧାନ- ଧାନ?       $ନା=0$        $ନା=2$

୧୦୧) ସାମ୍ପ୍ରତିକ ବିବରଣ:

କ) ଧାନ କିଲୋଗ୍ରାମ ଟିଆରୀ:       $ନା=0$       ବାସନ୍ତ = ୨,      ଚାଉଁଶ/ଚାଉଁଶର ଓଡ଼ିଆ = ୩,      ଚାଉଁଶର ଓଡ଼ିଆ/ପାଣିର ଓଡ଼ିଆ = ୫  
 ଗ୍ରୀଷ୍ମ = ୫,      ଚାଉଁଶ = ୩,

ଖ) ଧାନ କିଲୋଗ୍ରାମ ଟିଆରୀ       $ନା=0$ ,      ବାସନ୍ତ = ୨      ଚାଉଁଶ = ୩,      ଚାଉଁଶର ଓଡ଼ିଆ/ପାଣିର ଓଡ଼ିଆ = ୫  
 ଗ୍ରୀଷ୍ମ = ୫,      ଚାଉଁଶ = ୩,

ଗ) ଧାନ କିଲୋଗ୍ରାମ ଟିଆରୀ       $ନା=0$ ,      ବାସନ୍ତ = ୨,      ଚାଉଁଶ = ୩,      ଚାଉଁଶର ଓଡ଼ିଆ/ପାଣିର ଓଡ଼ିଆ = ୫

ଘ) ଧାନର ଧାନ ଓ ବାସନ୍ତର କି ଧାନର ଧାନ ଅନ୍ତର୍ଜାତିକ?       $ନା=0$ ,       $ନା=2$

২০. আপনি কি গতকাল কোন প্রকার ভিটামিন বা ও জাতীয় ঔষধ খেয়েছেন ?  
হ্যাঁ = ১ না = ২ জিনি না = ১

২০ক। আপনি বলতে পারেন কি ঘরনের ভিটামিন খেয়েছেন ?  
(উত্তরদাতা/দাত্রীকে প্যাকেট ছবি বা বোতল দেখানোর অনুরোধ করত হবে।)

২০খ। কিংও দুই সপ্তাহের মধ্যে আপনার কিছুর ভিটামিন জাতীয় ঔষধ খেয়েছে?  
হ্যাঁ = ১ না = ২ জিনি না = ১

২০গ। যদি খেয়ে থাকে তবে কি আপনি মেডিকেলের বিনা দিতে পারেন ?

২১। গতকাল আপনি বান্নাখ বত কাপ বা বত বোতল তেল ব্যবহার করেছেন?  
গোষ্ঠ কালের মধ্যে  অথবা গোষ্ঠ বত বোতল   
জিনি না = ১১ অথবা গোষ্ঠ বত চা-চামচ

২২। বতজন লোক গতকালের রান্না বত খাবার খেয়েছে ?

বয়স্ক (২৪ বয়সের ওপরে)   
কিন্তু (২৪ বয়সের নিচে)

